This study consists of two phases: (1) an intervention development phase wherein feedback from members of the target population will be used to iteratively refine the mHealth app and to convert the weight loss and sedentary behavior components of the intervention to a telecoaching model, and (2) a two group randomized controlled pilot trial (RCT) in 30 obese (BMI=30-45 kg/m²), low-active, older (55-85 years) adults with chronic pain randomized to either 12-weeks of active intervention or a wait-list control.

Objectives

The aim of this study is to develop and test the feasibility and acceptability of a novel, patient-centered intervention to reduce chronic pain in older adults, leveraging the combination of telecoaching and individually-adaptive mHealth tools to decrease both body mass and sedentary behavior. MORPH addresses the NIH's 2016 National Pain Strategy's call to: 1) expand non-pharmacological treatment options in older adults, who are particularly susceptible to the side effects of opioid and other pain medications; 2) develop accessible treatments that are individually-tailored; and 3) increase the development of self-management programs¹⁵.

Aims and Hypotheses

Specific Aim 1: To use an iterative user-centered design process to develop a mHealth application, to adapt the weight loss and sedentary behavior components of the intervention to a telecoaching model, and to evaluate the usability and feasibility of the intervention for obese, older adults with chronic pain.

Hypothesis 1: As a result of the iterative, person-centered design process, we expect scores on the system usability scale¹⁶ to improve across the development period. We expect fewer alterations to be required as the development process proceeds, and we expect fewer use and usability issues to present during the inhome trial. Note that data collected during this period will largely be qualitative in nature.

Specific Aim 2: To conduct a pilot RCT to provide initial evidence for the effect size associated with the proposed intervention on pain and physical function and to estimate the sample size needed for a RCT that is designed to compare the effects of the intervention versus usual care on pain ratings and physical function.

Hypothesis 2: We expect the provision of the in-home application to contribute to significant improvements in pain ratings and physical function compared to the usual care condition.

Methods and Measures

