Research participation	Willing to provide informed consent; Agree to all study procedures and assessments; Able to provide own transportation to study visits; owns an Android or Apple smartphone.	Current participation in other research study targeting pain, physical activity, or weight loss	Self-report				
Pain Status	Pain in 2 or more of the following sites on most days for the previous 3 months: back, neck, shoulders, hips						

	and/or knees		
Surgery		Joint replacement or orthopedic	
		surgery within previous 6 months	
		or planning to have orthopedic	
		surgery in the next 6 months	

age, weight, height, current physical activity habits, body weight in the past year, medical history, current medications, and eligibility to participate. All participants must conform to the study's inclusion/exclusion criteria. All participants, with questions regarding medical history will be cleared by a study physician (AB) and then will be approved for participation by study PI

Those who pass phone screening will be scheduled for a 1:1 development session (Phase I) or screening-visit (Phase II) at a WFBMC-affiliated facility. The screening visit will allow participants to complete self-reported questionnaires and tests of physical function. During both phases, participants provide written informed consent and complete a HIPAA authorization form in accordance with our IRB policy prior to collection of any data. For both phases, the first visit begins with measurement of weight and height to calculate BMI. Individuals who meet the BMI criteria will undergo a medical history and a cognitive test (MoCA¹⁹). The medical history (including blood pressure) will exclude those not meeting inclusion criteria with regard to medication use, health status, or cognitive status. Eligible participants will be randomized to treatment using a web-based randomization scheme, stratified by sex with random block sizes.

Study Procedures

A timeline for phases I and II is provided below.

Phase I – Person-Centered Design and Development

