improvements made to the interface following each small grouping of interviews (n=1-3 interviews). Finally, after the interview session, the participant will bring all study peripherals to their home (i.e., Fitbit device, connected scale), and engage with the app for one week. During this period, the participant will also complete one burst of ecological momentary assessment. Following this one-week period, the participant will return to the research site to return equipment, complete the System Usability Scale ¹⁶, and receive remuneration for their time. This process is to be completed iteratively until the investigative team is confident that no further iterations are needed, and participants no longer provide meaningful interface critiques.

Phase II - MORPH Pilot Study

Whereas Phase I is concerned with ensuring the usability and desirability of the application for the target population, Phase II is meant to establish the efficacy of the program when delivered in the home. Accordingly, Phase II is a randomized controlled pilot study in which participants (N=30) will enter the study in up to three small waves. We will begin with a trial run of ~5 individuals who will all be assigned to the intervention condition to pilot all facets of the intervention. For the duration of each wave, intervention staff will keep detailed notation of software and usability challenges, and iterations will be made in between waves. Notably, these iterations will not affect the overarching structure of the intervention, but will ensure all components of the program are maximally usability for the older adult with chronic pain. The participants that are not randomized to active intervention after screening will receive monthly phone calls to keep them engaged in the study until they return for the follow up visit.

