Content of Weight Loss (WL) & Sedentary Behavior (SB) Intervention. In sum, the MORPH pilot study is a 12-week randomized controlled trial. The MORPH app is embedded in a 9-week telecoaching intervention that is prefaced by 3 weeks of 1.5-hour group sessions for a total intervention spanning 12 weeks, plus 2 pre-study orientation appointments. The 3 weeks of initial face-to-face contacts are used to (a) establish the group-mediated nature of the telephone coaching contacts. (b) create connection between group members that will be built upon via the app, (c) teach basic skills needed for successful weight loss and reduced SB (e.g., mindfulness, food tracking, use of the app), and (d) develop competence in use of the mHealth app. The WL component targets a 3-5% reduction in body weight. The SB component targets: (a) increasing the number of postural shifts across the day, and (b) increasing the performance of valued activities related to independent living, including balance, strength, and mobility activates that will augment caloric restriction to promote WL and increase functional capacities as assessed by the short physical performance battery (SPPB). The distal goal of the activity component is to increase steps across the day in the range of 5,000 to 10,000 steps based on individual abilities. Individual goals for caloric intake will be prescribed to achieve an energy deficit of ~400 kcal/d from daily weight maintenance energy requirements (resting energy expenditure x activity factor of 1.3 for sedentary adults). The lowest caloric goal prescribed will be 1100 kcal/d for women and 1200 kcal/d for men. The content for the dietary weight loss intervention is based on our extensive experience in community-based trials and our most recent materials from CLIP-II, whereas the SB intervention builds upon the protocol we are using in EMPOWER (R01 AG051624-01) and has efficacy in preventing weight regain as evident from our published work with older adults¹⁰. Adaptation of these materials to the telecoaching + mHealth model will occur in Phase I.

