For Specific Aim 1 (development of mHealth application), we will use simple descriptive statistics and qualitative data to evaluate usability and feasibility of the intervention. For Specific Aim 2 (pilot RCT), the goal of the analysis is to (1) estimate the effect size of the intervention such that the results can be used to power a future larger RCT, and (2) explore appropriate methods and models for analyzing EMA/EMI data. We plan to estimate the effect size using the following generalized linear model: $Y_{FU} = \beta_0 + \beta_1 Y_{BL} + \beta_2 Int + \text{covariates} + \varepsilon$, where Y represents the primary outcomes (SPPB score, PROMIS pain scales), subscripts FU and BL denote measurement at week 12 follow up and baseline respectively. Intrepresents intervention status, \Box represents regression coefficient, and ε represents random error. Because of the small sample size, we may include important covariates (e.g., gender, age) into the model if the two arms happen to be highly imbalanced. In case covariates are used, effect sizes will be estimated using the adjusted values from the above equation. We also plan to conduct similar analyses of secondary outcomes of the RCT (e.g., WL & sedentary behavior) using the aforementioned model and apply the appropriate model link function if the secondary outcome is not continuous. Although our primary goal is to determine feasibility and effect size using data collected from baseline and week 12, we do recognize the potential value of the intensively collected EMA data. Exploratory analyses, including visualization will be used to study the utility of EMA data, which include both pain and psychosocial variables. For example, we will determine if preliminary evidence supports the crosslagged reciprocal relationship between pain and self-efficacy. Another example is the examination of intra-person vs inter-person variation in the EMA variables. The exploratory analysis is expected to inform the analytic plan for a future larger study.

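### Only the intervention arm is group-delivered, yet the Aim 2 model has one error term: if outcomes correlate within groups, intervals are too narrow, and a future sample size without a design effect is too small

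*Combined protocol and SAP*

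**What the plan says.** **Delivery.** Under Content of Weight Loss (WL) & Sedentary Behavior (SB) Intervention, the telecoaching is "prefaced by 3 weeks of 1.5-hour group sessions for a total intervention spanning 12 weeks". One purpose of the face-to-face weeks is to "establish the group-mediated nature of the telephone coaching contacts"; another is to build ties between members that the app then extends. Under Phase II - MORPH Pilot Study, participants "will enter the study in up to three small waves", software is revised between waves, and controls receive monthly calls until their follow-up visit. The assessment table places the controls' own intervention at weeks 17-29, after the primary endpoint.

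**Randomisation.** Participants are randomised individually, "stratified by sex with random block sizes" (Participant Screening and Randomization). Neither group nor wave is a stratum.

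**Analysis.** Under Statistical Analyses, follow-up is regressed on baseline, intervention status and optional covariates (gender and age are the examples), with a single random error. There is no group term, random effect, cluster-robust standard error, ICC or design effect.

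**Use.** The goal is to "estimate the effect size of the intervention such that the results can be used to power a future larger RCT", and Specific Aim 2 includes the task "to estimate the sample size needed for a RCT". Hypothesis 2 expects significant improvement. The plan states no alpha, no confidence interval and no formula for sizing the later trial.

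**The concern.** Up to week 12 this is a partially nested design: intervention participants are treated in groups and controls are not. Influence between members is an intended mechanism, and software changes between waves add a second source of shared variation that reaches only the treated arm. If outcomes within a group are positively correlated, the treated arm carries less independent information than its head count suggests, and the planned model cannot see this.

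Two outputs are exposed. One is any interval or test attached to the intervention coefficient. The other is the sample size for the next trial, which is a named product of Aim 2. A group-delivered programme sized with an individual-level variance has less power than intended.

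**Working it through.** The plan gives no power, precision or sizing calculation, so there is no figure to reproduce.

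**Inputs from the documents:** N=30 in total; two arms; up to three waves; group delivery in the intervention arm only before follow-up; one error term.

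**Assumptions, not in the documents:** 1:1 allocation (15 per arm); one group per wave; ICC 0.01, 0.05 and 0.10; equal total variance in both arms; no dropout. The plan also leaves open whether the trial run of about 5 non-randomised people counts toward the 30.

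**Step 1. Standard error in the pilot.** With group size m, the design effect in the treated arm is DE = 1 + (m-1) x ICC. The variance of the arm difference is proportional to DE/n_int + 1/n_ctl, whereas the model uses 1/n_int + 1/n_ctl. With equal arms the variance ratio is VR = (DE + 1)/2, and the ratio of true to model SE is sqrt(VR).

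Example, m=5, ICC 0.10: DE = 1 + 4 x 0.10 = 1.40; VR = 2.40/2 = 1.20; sqrt(1.20) = 1.10.

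| Treated groups | ICC 0.01 | ICC 0.05 | ICC 0.10 |
|---|---|---|---|
| three of 5 | 1.01 | 1.05 | 1.10 |
| two of 7-8 (m = 7.5) | 1.02 | 1.08 | 1.15 |
| one of 15 | 1.03 | 1.16 | 1.30 |

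**Step 2. Simulation of the planned model** (10,000 runs per case; true effect 0.50; assumed baseline correlation 0.6). Coverage of a nominal 95% interval:

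| Treated groups | ICC 0 | ICC 0.05 | ICC 0.10 |
|---|---|---|---|
| three of 5 | 94.7% | 93.6% | 92.5% |
| two of 8 | 94.7% | 93.0% | 91.0% |
| one of 15 | 95.1% | 91.5% | 86.8% |

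The mean estimate stayed between 0.497 and 0.506, so ignoring the grouping does not bias the point estimate.

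**Step 3. Scale against N=30.** With 15 per arm and 27 residual degrees of freedom, the 95% half-width is about 0.75 residual SD. With three groups at ICC 0.10 it becomes 0.75 x 1.095 = 0.82. The estimate is very imprecise either way.

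**Step 4. Sizing the next trial.** For illustration, take a standardised effect of 0.5, two-sided alpha 0.05 and 80% power (all assumed). Under independence this needs 63 per arm. The required number becomes 63 x VR, and power at 63 per arm is Φ(0.5/sqrt(2 x VR/63) - 1.96).

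Example, groups of 10, ICC 0.10: DE = 1.90; VR = 1.45; sqrt(2.90/63) = 0.2145; 0.5/0.2145 - 1.96 = 0.37; Φ(0.37) = 0.64.

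| Future group size | | ICC 0.01 | ICC 0.05 | ICC 0.10 |
|---|---|---|---|---|
| 5 | n per arm needed | 65 | 70 | 76 |
| 5 | power at 63 per arm | 79% | 76% | 73% |
| 10 | n per arm needed | 66 | 78 | 92 |
| 10 | power at 63 per arm | 78% | 72% | 64% |

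**Step 5. Can the pilot estimate the ICC?** No. With three groups of 5, an estimate of 0.05 has a 95% interval of about -0.18 to 0.91. With one group, the group effect cannot be separated from the treatment effect.

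**The case against.** A reader might infer that the pilot's interval is definitely too narrow and that the future trial will be undersized. The documents support neither.

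- The plan names no interval. Independence is implied by the single error term, and the shortfall exists only if the ICC is above zero. No ICC is given, and much of the delivery is individual: personal activity baselines, weekly goals set by email, tailored feedback and prompts. Correlation is plausible, but its size is unknown.
- Undersizing does not follow from the pilot model. The point estimate is unbiased, and the next trial is too small only if its sizing also omits a design effect. The documents give no formula, power or group size for that trial, and silence about a later protocol is not a decision to omit.
- One group per wave is an assumption. At ICC 0.01 the SE shortfall is only 1-3%. With 27 degrees of freedom the estimated SE itself varies by about 26% either way, so a 1-10% shortfall with three groups is well within the noise.
- One to three groups cannot support a random group effect.

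The first three points stand, and they limit the claim to a conditional one. The last rules out estimating the ICC, but not working with a fixed range. Nor do these points remove the sizing issue: the future sample size is something this trial undertakes to report, and nothing in the plan alerts its user to group delivery.

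**Conclusion.** The point holds in conditional form. Treatment before week 12 is grouped in one arm only, and the Aim 2 model makes no allowance for it. If the ICC is above zero, any interval or test is too narrow, and a sample size taken from Aim 2 without a design effect is too small. The effect estimate itself is not biased.

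For the pilot's own interval the matter is minor with three groups, moderate with two, and substantial with one, which the wording on waves permits. The sizing consequence carries more weight: in the illustration, the power lost from a planned 80% ranges from about 1 point (groups of 5, ICC 0.01) to about 16 points (groups of 10, ICC 0.10). All of these sizes rest on the assumed ICC, group sizes, allocation, effect and power.

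**What to change.** 1. Keep the ANCOVA point estimate. Record the actual number and size of treatment groups, and state whether the trial-run participants enter the model.
2. Report a sensitivity interval with SE = s x sqrt(DE/n_int + 1/n_ctl), for ICC 0.01, 0.05 and 0.10. Here s is the ANCOVA residual SD, DE = 1 + (m-1) x ICC, m is the size-weighted mean group size (sum of squared sizes over sum of sizes; groups of 7 and 8 give 113/15 = 7.5), and the ICC is on the baseline-adjusted scale.
3. Apply the same one-arm design effect, at the planned group size, to the future sample size that Aim 2 reports.
4. Do not estimate the ICC from one to three groups. If there is only one group, say that its effect cannot be separated from that of treatment.

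**Cost.** A short table and a sentence or two, with no new data. The sensitivity interval is about 1-15% wider with two or three groups and up to about 30% wider with one, and the reported future N is larger. The correction is slightly too small, because s itself shrinks a little when groups differ: with one group at ICC 0.10 the simulated ratio of true to model SE was 0.383/0.287 = 1.33, against 1.30 from the formula.

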Ecological momentary assessment (EMA; assessments collected in near real time and in the real world²⁴) will be utilized to (a) gain insight into the relationships between key daily health behaviors (sleep, diet, activity) and pain and fatigue; (b) provide highly personalized feedback following the first week of each month on the relationships between an individual's health behaviors and their pain and fatigue responses across the day; and (c) guide the delivery of just-in-time mindful movement prompts. To minimize participant burden, we will use 1-week EMA bursts during weeks 1, 5, and 9. During each burst, participants will receive approximately 6 brief (i.e., <60 seconds) daily assessments delivered via smartphone within 2-hour intervals throughout waking hours, and will report current level of pain (on an 11-point Likert scale) and affect (the Feelings Scale²⁶), as well as whether any medications had been taken since the previous survey. These variables can be expected to influence SB and eating patterns, along with previous night's sleep duration and quality, which will be reported on the first assessment of each day (assessed via items from the Pittsburgh sleep quality index²⁷). These assessments will be used to identify daily risk periods: "pain peaks" and "affect troughs". We expect these two variables in particular to contribute to higher levels of SB and unhealthy eating ^{14,28}. These daily risk periods will be identified in feedback to the participant, and will also be used to craft "awareness alerts". Specifically, these data will be utilized by the program staff to create up to two daily Fitbit silent alarms. These prompts aim to cue the participant to both be mindful of their current state, and to engage in brief mindful-based exercises which are practiced in weekly telecoaching sessions—to improve affect, reduce pain, and prevent overeating or extended sitting. The aim is to set prompts prior to daily pain periods and/or sitting period to encourage movement to suppress sitting-related stiffness and pain. These prompt schedules will be updated automatically with each EMA burst, and participants will have the opportunity to manually alter the timing of daily prompts. Those in the wait listed control condition will also complete EMA bursts on the same schedule as those in the intervention arm, and these will provide insight into the effect of the intervention on daily behaviors and trajectories of pain and fatigue.

Device Use

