Because device ownership is a requirement for this study, those who lose access to the device during the intervention will be noted, but will be asked to return for post-study assessments. We are not, however, able to provide a device. All participants will be provided a Fitbit and connected scale for the purposes of the study. If the Fitbit is lost, stolen, or damaged, participants will be provided with a replacement. If a participant withdraws from the study, they will be asked to return the Fitbit. After completion of the last study visit, participants will be allowed to keep the Fitbit, as the devices become worn with time. The connected scales and ActivPal will be returned to the research center upon completion of the study.

Study Assessments

During Phase I, study assessments occur during the primary study visit (P1V1), and again after completion of the one-week trial (P1V2)

During Phase II, study assessments occur during a baseline physical function and questionnaire appointment (P2V1), and a technological orientation (P2V2). Note that no measures are collected during

the P2V3 nutrition appointment. Final assessments are collected during the final week of the intervention or following the intervention (P2V4). A table of assessments collected during Phase II is provided below.

MORPH Measures	Outcome	P1V1	P1V2	P2V1	P2V2	P2V3	P2 Intervention	P2 Weeks 1,5,9, 12	P2V4	P2V5 *Control only	P2V6 *Control only	P2 Control Inter- vention
Week		0	1	0	0		1-12	1,5,9,12	12-14	15	16	17-29
A/B Preferences	Primary Non-RCT*	X										
Retrospective Think Aloud Coding	Primary Non-RCT*	X										
System Usability Scale	Primary Non-RCT*		X									
Issue Logs	Other		X				X					X
Demographics & Medical History	Other	X		X								
MOCA	Other	X		X								
Adverse Events	Other		X				X		X			X
CES-D	Other	X		X					X			
FACIT	Other	X		X					X			
Pittsburgh Fatigability	Other	X		X					X			
Pittsburgh Sleep Quality Index	Other	X		X					X			
SF-36	Other	X		X					X			
Satisfaction with Physical Function	Other	X		X					X			
Self-Efficacy for Walking	Other	X		X					X			
Movement Self- Efficacy	Other	X		X					X			
Self-Efficacy for Managing Eating	Other	X		X					X			
MAAS	Other	X		X					X			
Power of Food	Other			X					X			
Food Cravings	Other			X					X			
Perceived Stress	Other	X		X					X			
Body Weight	Secondary	X		X					X			

II : 1 / DD D I	0.1	37	37				37			
Height, BP, Pulse	Other	X	X				X			
PROMIS Pain	Primary	X	X				X			
Intensity Scale (3	*RCT Phase									

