item)										
PROMIS Pain	Primary	X	X				X			
Interference Scale	*RCT Phase									
(8 item)										
Short Physical	Primary		X				X			
Performance	*RCT Phase									
Battery (SPPB)										
Mobility	Other		X				X			
Assessment Tool										
Short Form (MAT-										
SF)										
In-Home Weight	Other				X				X	
(Connected Scale)										
Sedentary Activity	Secondary		X				X			
& Transitions										
(ActivPal)										
Steps, Light and	Secondary			X		X				
Vigorous Activity						*only week				
(ActivPal)						12				
Sedentary Activity	Other	X			X				X	
& Transitions										
(Fitbit)										
Steps, Light and	Other	X			X				X	
Vigorous Activity										
(Fitbit)										
Daily Pain (EMA)	Other	X		X	X	X			X	
Daily Affect (EMA)	Other			X		X				
Medication used?	Other			X		X				
(EMA)										
App Use (count)	Secondary				X					
Retention	Secondary						X			
L			l .			1 1		1		1

Study Measure(s)

- 1. Baseline demographic data will be recorded based on participant self-report. Medical information on prior and existing co-morbidities and hospitalizations will be ascertained by self-report and confirmed by direct query of the participant at the screening visit. We will also record medication use by asking participants to bring in all medications (including nutritional supplements).
- 2. Adverse events will be assessed by asking participants at each assessment visit, and during weekly telecoaching calls. Participants will be asked to report any health changes, injuries, etc. and these will be recorded using the Adverse Event Form.
- 3. Physical function (a primary outcome of this study) will be assessed using the Short Physical Performance Battery (SPPB¹⁸), which is a measure of lower-extremity function consisting of walking speed, balance, and repeated chair stands. Perceptions of physical functioning will be assessed using the Mobility Assessment Tool Short Form (MAT-SF²⁹).
- 4. Pain (the second primary outcome of this study) will be assessed using the PROMIS¹⁷ pain intensity (3 item) and pain interference (8 item) scales.
- 5. Body weight: Body weight will be measured in-clinic on the same scale. As a process measure, we will also obtain body weights weekly from individuals in-home using a connected scale.

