- 12. Ecological Momentary Assessment: EMA will be used to study within-person and within-day interactions between sleep quality and duration (assessed via items from the Pittsburgh Sleep Quality Index²⁷), affect (assessed via the feelings scale), and level of pain.

During weeks 1, 5, and 9, participants will complete week-long daily assessments. Participants will be instructed to complete assessments upon waking up in the morning and immediately prior to going to bed at night. Additionally, each participant will receive up to five daily text message prompts with links to secure web-based questionnaires. Each assessment will take the average user less than one minute to complete, and will contain all items with the exception of sleep items, which will be assessed only during the first assessment of the day.

- 13. App Use: We will note how many times the app is opened from the home screen throughout the study.
- 14. Retention: We will record retention as the number of consented participants who complete baseline and follow-up testing.

Statistical Analyses

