Informed Consent: The informed consent process will follow the procedures of the WFSM Institutional Review Board. The potential participant is mailed the informed consent form and asked to read it before their initial visit. The form is written in simple, easy-to-understand language. At first contact with the prospective participant during the initial visit, the study staff member will explain the purpose, methods and extent of the study. We require study staff to review all of the key aspects of the study verbally with the potential participants and to question potential participants to ascertain whether s/he has understood the information. Potential participants are encouraged to ask questions regarding the consent form and the study. A copy of the signed and dated consent form will be given to participants, and the original document will be placed in their individual study file, which will be stored in a secure location. In compliance with the Health Insurance Portability and Accountability Act (HIPAA) and the Standards for Privacy of Individually Identifiable Health Information of the Department of Health and Human Services, we will access personal health information only after obtaining informed consent.

Potential Study Risks: There are inherent potential risks to human subjects who participate in any research study and the potential risks to study participants in this study are listed below. Any injuries or illnesses (adverse events) during the course of a participant's enrollment in the study are monitored regularly.

- Physical function tests: There is a small risk of injury during the physical function tests, such as muscle strains or pulls, falls, or joint injury. Risks will be minimized by having experienced/trained staff conducting these assessments. A warm-up and range of motion practice will be conducted before testing. If a participant reports pain, dizziness, or other medical problem, the test will be terminated.
- Weight loss at any age include the concomitant loss of lean (muscle and bone) tissue along with fat mass loss. However, the clinical impact of this muscle and bone loss is not known. Since most adults with obesity have a higher muscle mass and bone density, this risk is mitigated by excluding individuals who are non-obese and less likely to benefit from weight loss.

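### Wait-list controls have no specified adverse-event question between baseline and P2V4, while the intervention arm is asked weekly

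*Combined protocol and SAP*

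**What the plan says.** - **How events are asked about.** Study Measure(s), item 2: adverse events "will be assessed by asking participants at each assessment visit, and during weekly telecoaching calls". No other contact is named.
- **Intervention arm, weeks 1-12.** The section on the content of the weight loss and sedentary behavior intervention describes a "9-week telecoaching intervention that is prefaced by 3 weeks of 1.5-hour group sessions".
- **Wait-list controls, weeks 1-12.** Under Phase II - MORPH Pilot Study, those not randomised to active intervention "will receive monthly phone calls to keep them engaged in the study until they return for the follow up visit".
- **EMA.** The Ecological Momentary Assessment section adds: "Those in the wait listed control condition will also complete EMA bursts on the same schedule as those in the intervention arm".
- **Schedule of assessments.** The Adverse Events row is marked for Phase II under P2 Intervention (weeks 1-12), P2V4 (weeks 12-14) and P2 Control Intervention (weeks 17-29). It is blank at P2V1 and P2V2 (both week 0), at P2V3, and in the column for weeks 1, 5, 9 and 12.
- **General statement.** Under Potential Study Risks, events during a participant's "enrollment in the study are monitored regularly".
- **Reporting.** Minor events are to be recorded and reported within seven days. The investigators and medical director review events quarterly and report them in aggregate.

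**The concern.** The rule in item 2 attaches the adverse-event question to a contact that controls do not have during the randomised period. A control who has a minor event in that period, such as a fall without injury, is not due to be asked about it until P2V4. By then the event may be forgotten or hard to date, and the seven-day rule cannot start until staff know of it. The plan lists falls as a risk of the movement component and counts non-injurious falls at screening, so minor falls are events it cares about.

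The second issue is comparability. More frequent asking tends by itself to bring out more minor self-reported events. If events were ever tabulated by arm, the intervention arm would tend to look worse for that reason alone, and its falls would have no usable background rate beside them.

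**Working it through.** **1. The plan's own figure.** 9 weeks of telecoaching + 3 weeks of group sessions = 12 weeks, which agrees with the stated total. Sessions are weekly, so there are 9 telecoaching calls, taken here as weeks 4-12.

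**2. Specified queries after baseline.**
- Intervention arm: 9 calls + P2V4 = 10. If the weeks 1-12 mark in the schedule also covers the group sessions, 9 + 3 + 1 = 13.
- Controls: no telecoaching and no assessment visit before P2V4, so 0 + 1 = 1.

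**3. Whether another control contact fills the gap.**
- The monthly calls are given a retention purpose only, with no adverse-event question.
- The EMA sections list pain, affect, medication and sleep. Item 12 says each assessment "will contain all items with the exception of sleep items", which are asked once a day. None of these is an adverse-event item, and the Adverse Events row is blank in the column matching the EMA weeks.
- The instruction to log skin irritation and phone staff if it is troublesome concerns the activity monitors. It does not cover falls, other injuries or illness.
- The statement about regular monitoring names no contact, question or frequency.

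**4. Wait from event to next specified query.** Assume events are uniform over weeks 0-12. For events in an interval of length L, with the next query g weeks after the interval ends, the mean wait is L/2 + g. Intervals are weighted by L/12.

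| Arm and query weeks | Mean wait (weeks) | Maximum | Share over 4 weeks |
|---|---|---|---|
| Intervention, 4 to 12 weekly | (4/12)(2) + (8/12)(0.5) = 1.0 | 4 | 0% |
| Intervention, 1 to 12 weekly | 0.5 | 1 | 0% |
| Controls, P2V4 at week 12 | 12/2 = 6.0 | 12 | 8/12 = 67% |
| Controls, P2V4 at week 14 | 12/2 + 2 = 8.0 | 14 | 10/12 = 83% |

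**5. With the form used on control calls.** The plan gives no call weeks; weeks 4 and 8 are assumed.

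| Control query weeks | Mean wait (weeks) | Maximum | Share over 4 weeks |
|---|---|---|---|
| 4, 8, P2V4 at 12 | 4/2 = 2.0 | 4 | 0% |
| 4, 8, P2V4 at 14 | (1/3)(2) + (1/3)(2) + (1/3)(2 + 2) = 2.7 | 6 | 2/12 = 17% |
| 4, 8, 12, P2V4 at 14 | 2.0 | 4 | 0% |

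**The case against.** The strongest reply is that the gap is one of documentation. The P2 Intervention column is not labelled as intervention-arm only, although P2V5 and P2V6 are labelled as control only. It could denote the 12-week period, in which case its adverse-event mark covers controls. The monthly calls have a stated purpose but no stated script, so staff may well ask about health. The statement about regular monitoring is not limited to one arm. Participants may also have been told to report injuries themselves; the consent form was not available for this check.

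Part of this stands. Staff may ask, and the waits above run to the next specified question, not to detection. They would equal detection delays only if no control mentioned an event sooner. No event rate is available, so the number of late or missed events in a 30-person pilot cannot be estimated. The seven-day rule is not contradicted either: it gives no clock start, and the intervention arm can itself wait up to 4 weeks on the narrower count.

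The column reading does not remove the gap. Controls have their own P2 Control Intervention column at weeks 17-29. Even if the earlier mark is taken to include them, item 2 still names no contact in weeks 1-12 at which they would be asked.

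It is also fair that closer monitoring of the arm receiving the programme is reasonable. Item 2 can keep that and still ask controls something.

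**Conclusion.** The concern holds. As written, the plan specifies 10 adverse-event queries after baseline in the intervention arm (13 on the wider reading) against 1 in controls, who go unasked for 12 to 14 weeks. These counts come directly from the text. The mean waits (0.5-1.0 against 6.0-8.0 weeks) and the shares waiting more than 4 weeks (0% against 67%-83%) also rest on the uniform-event assumption and on the timing of P2V4.

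The consequence is limited. Statistical Analyses models the primary and secondary outcomes and plans no between-arm comparison of safety, events are reported in aggregate, and serious events are likely to be less affected. The effect-size and feasibility aims do not depend on this. It should still be corrected, because the rule as written gives controls no means of being monitored regularly during the randomised period.

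**What to change.** 1. Administer the existing Adverse Event Form at the monthly control calls.
2. Amend item 2 to name those calls as a third occasion for wait-list controls, alongside assessment visits and telecoaching calls. Show this for controls in weeks 1-12 in the Adverse Events row of the schedule, and label which arm each mark covers.
3. Only if events are ever shown by arm: state that the intervention arm was also asked weekly, and show separately the events elicited only on weekly calls.

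**Cost.** The calls and the form already exist, so steps 1 and 2 should need only a few more minutes per call and two text edits, with no new visits or forms. The documents give no call length or staffing, so the time is a judgement. Step 3 needs a note of the contact at which each event was reported.

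**Remaining limit.** Controls would have 3 or 4 specified queries against 10 or 13, so ascertainment would be closer but not equal.
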